3.1 Inclusion Criteria

Patients should meet all of the following criteria at the time of registration:

- 3.1.1 Have signed an informed consent document indicating that the subject understands the purpose of and procedures required for the study and are willing to participate in the study.
- 3.1.2 Be willing and able to adhere to the prohibitions and restrictions specified in this protocol.
- 3.1.3 Males 18 years of age and above.
- 3.1.4 Eastern Cooperative Group (ECOG) performance status ≤ 1 .
- 3.1.5 Patient must have progressive disease while receiving androgen deprivation therapy (ADT) defined by any one of the following as per the PCWG3 criteria for PSA, measureable or non-measurable (bone) disease and must have a castrate serum testosterone level (i.e. ≤ 50 ng/dL) at screening:
 - 3.1.5.1 PSA: At least two consecutive rises in serum PSA, obtained at a minimum of 1-week intervals, with the final value ≥ 2.0 ng/mL.
 - 3.1.5.2 Measurable disease (by RECIST 1.1): $\geq 20\%$ increase (with an absolute increase of at least 5mm) in the sum of diameters of all measurable lesions or the development of one or more new lesions. The short axis of a target lymph node must be more than 15mm to be assessed for change in size.
 - 3.1.5.3 Non-measurable (bone) disease: The appearance of two or more new areas of uptake on bone scan consistent with metastatic disease compared to previous imaging during castration therapy. The increased uptake of pre-existing lesions on bone scan will not be taken to constitute progression, and ambiguous results must be confirmed by other imaging modalities (e.g. X-ray, CT or MRI).
- 3.1.6 Documented histologically confirmed adenocarcinoma of the prostate.
- 3.1.7 Metastatic prostate cancer (M1) as documented by appropriate medical imaging (i.e. CT-Scan, PET scan or bone scan).

- 3.1.8 Treatment failure of either abiraterone and/or enzalutamide per PCWG3 criteria for PSA, measurable disease or non-measurable (bone) disease.
- 3.1.9 Willingness to use contraception by a method that is deemed effective by the Investigator throughout the treatment period and for at least 30 days following the last dose of therapy.
- 3.1.10 Willingness and ability to comply with study procedures and follow-up examination.
- 3.1.11 Able to swallow and retain oral medication.
- 3.1.12 Willingness and ability to undergo mandatory tumor biopsy at baseline and week 8/cycle 3.
- 3.1.13 Willingness and ability to undergo mandatory whole blood sample collections at baseline, days 8, 15, and 22 in the first cycle, and then monthly.

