8.2.1 PSA

In this study, PSA testing is being performed on days 8, 15, and 22 of Cycle 1, Day 1 of Cycle 2 and each subsequent cycle (every 4 weeks) with the threshold PSA level at 2.0 ng/mL. To report PSA-based outcomes, PCWG3 recommends that the percent of change in PSA from baseline to 8 weeks (or earlier for those who discontinue therapy) and the maximum decline in PSA that occurs at any point after treatment be reported for each patient using a waterfall plot.³ Because the rate of rise has shown prognostic significance, estimate a pretreatment PSA doubling time (PSA-DT) if at least 3 values are available, but do not delay either treatment or enrollment onto a trial simply to estimate PSA-DT. Because declines in serum PSA, if they occur, may not do so for several weeks, PSA measurements obtained during the first 8 weeks should not be used as the sole criterion for clinical decision making.

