9.3 The association of AR signaling with Exceptional Response to ESK981

Furthermore, since modulation of androgen receptor (AR) signaling through tyrosine kinases is observed as a mechanism of resistance to androgen deprivation therapy and androgen-independence, we hypothesize that the loss of dependence on AR signaling will be an additional independent predictor of response and outcomes. The trial is designed to enrich for AR-independent patients in the Enza/Abi-refractory cohort who will allow us to evaluate our hypotheses. Aggregate scores of AR-dependence and AR-independence will be derived from the expression levels of canonical AR targets and trans-differentiation markers.

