11.2 Endpoints

11.2.1 The first primary endpoint (PSA50) is a PSA decline of $\geq 50\%$ from baseline (PSA50), using the PCWG3 criteria. Refer to Section 8.2.1.

The second primary endpoint(s) (toxicities) is (are) defined in Section 7. Adverse events of all grades will be captured by the National Cancer Institute - Common Terminology Criteria for Adverse Events, version 4.03 (NCI-CTCAE v4.03) and GCP standards.

11.2.2 The secondary endpoints are defined as follows:

Time to PSA response (TTPR) is defined as the time from treatment start until the first documented occurrence of PSA50. PSA50 is defined in Section 1.3.

Duration of PSA response (PRD) is defined as the time from start of PSA50 until PSA progression (defined in Section 8.3.2).

PSA progression free survival (PPFS) is defined in Section 8.3.2 except that it will be based on PSA assessments only. PSA progression rates will be estimated from the PSA-only PFS distribution.

11.2.3 The correlative/exploratory/tertiary endpoints (and the methods of their determination) are described in Section 9.

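### Men who qualify by scan have no minimum baseline PSA but still count in the PSA50 rate, and the 2.0 ng/mL threshold in Section 8.2.1 is undefined

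*Combined protocol and SAP*

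**What the plan says.** **Entry.** Section 3.1.5 accepts progression "defined by any one of the following as per the PCWG3 criteria for PSA, measureable or non-measurable (bone) disease". The three routes are:

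- 3.1.5.1, PSA: consecutive rises "obtained at a minimum of 1-week intervals, with the final value ≥ 2.0 ng/mL".
- 3.1.5.2, soft tissue: a RECIST increase "in the sum of diameters of all measurable lesions or the development of one or more new lesions". No PSA value is required.
- 3.1.5.3, bone: "The appearance of two or more new areas of uptake on bone scan consistent with metastatic disease compared to previous imaging during castration therapy". No PSA value is required.

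Section 3.1.8 (failure of abiraterone and/or enzalutamide) can also be met on imaging alone. Section 3.2 contains no exclusion based on PSA.

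**Endpoint.** Section 11.2.1 states: "The first primary endpoint (PSA50) is a PSA decline of" at least 50% from baseline. It sets no absolute minimum and refers to Section 8.2.1. That section describes the PSA testing schedule "with the threshold PSA level at 2.0 ng/mL" and does not say whether the figure concerns entry, evaluability, scoring or progression.

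**Analysis set.** Section 11.3.4 builds the main (EEC) set from eligibility, at least 28 days on treatment, and at least 75% of pills taken in Cycle 1. Baseline PSA plays no part.

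**The concern.** The primary endpoint is a percentage change in PSA, so its meaning depends on where PSA starts. The plan sets a starting level for one entry route and leaves the other two open. A man with a PSA of 0.4 ng/mL who enters on a bone scan becomes a responder on a change of 0.2 ng/mL. A man whose baseline is undetectable has no percentage change to calculate, and the plan does not say how he is scored.

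The design has little room for doubtful classifications. It aims to show, in 27 patients, that the lower confidence limit exceeds a 20% reference rate, and its own planning case clears that value by only 0.001. An undefined threshold in the section that the endpoint cites also leaves room to settle who counts after the PSA data have been seen.

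**Working it through.** **Inputs.** From Section 11.3: N=27, planning rate 30%, reference rate 20%, one-sided 90% Wilson lower limit, stated limit 0.201. From Section 11.3.4: attrition 15%, 32 enrolled. The number of men entering with PSA below 2.0 ng/mL is not given, so any count used below is an assumption.

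**Step 1. Reproduce the plan.** With z = 1.2816,

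L = [p + z²/(2n) − z·√(p(1−p)/n + z²/(4n²))] / (1 + z²/n).

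For p = 0.30 and n = 27: (0.3000 + 0.0304 − 0.1170) / 1.0608 = **0.201**. This matches. Enrolment is 27/0.85 = 31.8, rounded up to 32. The sample-size figures are sound.

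**Step 2. Limits at attainable counts.** A rate of exactly 30% is not attainable with 27 men, so the neighbouring counts matter.

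| Responders | Calculation | Lower limit |
|---|---|---|
| 8/27 | (0.2963 + 0.0304 − 0.1167)/1.0608 | 0.198 |
| 9/27 | (0.3333 + 0.0304 − 0.1202)/1.0608 | 0.230 |

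Nine is the smallest count whose limit exceeds 20%. One patient is worth 1/27 = 3.7 points.

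**Step 3. Effect of leaving low-PSA men out.**

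- If the result is 8/27 and one non-responder had a low baseline, 8/26 gives (0.3077 + 0.0316 − 0.1202)/1.0632 = 0.206. The limit moves above 20%.
- If the result is 9/27 and one responder had a low baseline, 8/26 again gives 0.206. The reading does not change.
- If two of those nine had low baselines, 7/25 gives (0.2800 + 0.0328 − 0.1197)/1.0657 = 0.181. The limit moves below 20%.

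The with-and-without comparison can therefore change the reading in either direction.

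**Step 4. How much one such man could matter (illustration).** Suppose one of the 27 has a very low baseline and the other 26 respond independently at the rate shown. The chance of at least 9 responders is:

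| The low-PSA man | Formula | Others at 30% | Others at 20% |
|---|---|---|---|
| responds at the same rate as the rest | P(X≥9), n=27 | 0.423 | 0.074 |
| cannot respond | P(X≥9), n=26 | 0.373 | 0.059 |
| is certain to be counted as a response | P(X≥8), n=26 | 0.540 | 0.131 |

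If two or three men could not respond and the rest respond at 30%, the chance falls to 0.323 or 0.275. The expected rates are then 0.30 × 25/27 = 27.8% and 0.30 × 24/27 = 26.7%. These are extremes under assumed counts, not estimates. The sign depends on how such men behave, which the documents do not say.

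**Step 5. Sample size after the change.** With an entry floor, N stays at 27, enrolment at 32 and the planning limit at 0.201. If low-PSA men are enrolled but set aside and 27 evaluable men are still wanted, enrolment is 27/[(1 − m/27) × 0.85]. That is 33, 35 or 36 for an assumed m = 1, 2 or 3 low-PSA men in every 27.

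**The case against.** The best defence has four parts.

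1. A percentage fall can be calculated for any detectable baseline, so these men are scored. This stands. A reader might infer that such men can neither meet nor fail PSA50, but that is true only of an undetectable baseline. Otherwise the weakness is reliability.
2. Section 8.2.1 may have been meant as the missing rule. Its wording does not exclude that, but it does not establish it either. The fair criticism is that its purpose is unstated.
3. The design is based on precision and seeks preliminary evidence, with no formal go/no-go rule or stated power. This also stands. The 42% chance of reaching 9/27 comes from the choice of N and has nothing to do with the PSA floor. Section 11.3.2 does, however, read a lower limit above 20% as the sign of success, so crossing that value matters.
4. A floor might remove men of interest for the correlative aims. This is a real cost, and it is the reason for offering an evaluable-set alternative.

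The planned spaghetti plots of serial PSA would show low baselines, but they would not change or qualify the primary estimate.

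**Conclusion.** The gap is real: the 2.0 ng/mL floor covers one of three entry routes, nothing later in the plan closes it, and the 8.2.1 threshold is undefined. It is a cheap improvement and does not invalidate the design. Its size is bounded by the number of such men, at up to 3.7 points each. The documents give neither that number nor the net direction.

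Three stronger readings are tempting but unsupported:

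- **That PSA50 is biased downward.** The fall from 42% to 28% in the chance of 9 or more responders needs three men with no chance of response. If low-PSA men respond at 30% like the rest, the 42% does not move. If one is certain to be counted as a response, it rises to 54%.
- **That the problem will be common because of the target population.** Section 9.3 says "The trial is designed to enrich for AR-independent patients in the Enza/Abi-refractory cohort", but the documents nowhere link AR-independence to a low PSA.
- **That the floor would also mend PSA progression.** Section 8.3.4 requires both a 25% and a 2.0 ng/mL rise. The absolute part governs for any reference value below 8 ng/mL (2.0/0.25), so a 2.0 ng/mL floor leaves that feature in place. It is also the definition the protocol adopts, not a drafting slip.

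**What to change.** Settle one of the following before PSA50 is analysed.

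- **Entry floor.** Move the figure from 3.1.5.1 up to 3.1.5, for example: *Baseline PSA must be at least 2.0 ng/mL, whichever form of progression qualifies the patient.* This is one sentence using the protocol's own number. The cost is that a few men who progress only on scan are excluded, with slightly slower accrual.
- **Evaluable set.** If those men are wanted for the correlative aims, define a PSA50-evaluable set (baseline PSA at least 2.0 ng/mL) in Section 11.3.4, and say how an undetectable baseline is handled. Report PSA50 with its Wilson lower limit both with and without men below the floor. The cost is a few fewer men in the evaluable set, or the modest extra enrolment in Step 5 if 27 evaluable men are to be kept.

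In either case, state in Section 8.2.1 what the 2.0 ng/mL threshold governs and make it agree with Section 3.1.5. If men below the floor are already enrolled, give the with-and-without result for them.

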In a search for alternate MTKIs that could be re-positioned for the treatment of metastatic CRPC (mCRPC), we synthesized and evaluated ESK981 amongst a panel of other MTKIs. Interestingly, as our preliminary data will highlight, ESK981 exhibited nanomolar activity in the inhibition of prostate cancer cell line growth relative to other MTKIs tested including cabozantinib and crizotinib (both of which have been evaluated clinically in mCRPC). These early results piqued our further interest in deciphering the molecular basis for the log-fold increased sensitivity to ESK981 relative to other MTKIs in prostate cancer cells.

ESK981 is an orally active multiplex kinase inhibitor with favorable safety, pharmaceutical, ADME (absorption, distribution, metabolism, and excretion), and pharmacokinetic profiles. Clinical testing demonstrated linear dose-related oral exposure in humans with 8-15 h half-life and a high level of patients achieving stable disease at doses at or right below the expected Phase II dose. Our observation of a direct activity of ESK981 on prostate cancer cell autophagy coupled with its anti-angiogenesis activities provides a compelling rationale to investigate this MTKI in the treatment of mCRPC patients.

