7.5 Procedure in Case of Pregnancy

The effect of ESK981 in pregnant and lactating women is not known, and the exposure of a fetus or nursing infant is considered a potential risk. ESK981 can cause fetal harm when administered to a pregnant woman based on its mechanism of action. Subjects receiving ESK981 are advised to use two acceptable methods of birth control (one of which must include a condom as a barrier method of contraception) starting at the time of screening for an ESK981 study and continuing throughout the course of treatment and for at least three months after ESK981 is discontinued.

If, during the conduct of the clinical trial, a male subject impregnates his partner, the subject should report the pregnancy to the investigator. The investigator should report the pregnancy to the sponsor as an SAE within 24 hours of awareness of the event. The expected date of delivery or expected date of the end of the pregnancy, last menstruation,

estimated fertility date, pregnancy result and neonatal data etc., should be included in this information.

The investigator should report the outcome of the pregnancy (independent of outcome, e.g., full term delivery, pre-term delivery, spontaneous abortion, induced abortion, stillbirth, death of newborn, congenital anomaly [including anomaly in a miscarried fetus, etc.]) in accordance with the same reporting procedure as for SAEs. The date of outcome of the pregnancy, gestational age, date of birth and neonatal data etc., should be included in this information.

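### Inclusion criterion 3.1.9 checks a weaker contraception standard (one method, at least 30 days after the last dose) than section 7.5 advises (two methods including a condom, at least three months)

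*Combined protocol and SAP*

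**What the plan says.** Two current provisions of the combined protocol and SAP deal with contraception.

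- **Section 3.1.9 (Inclusion Criteria)**, which must be met at registration: "Willingness to use contraception by a method that is deemed effective by the Investigator", to be used "throughout the treatment period and for at least 30 days following the last dose of therapy".
- **Section 7.5 (Procedure in Case of Pregnancy)**: men receiving ESK981 "are advised to use two acceptable methods of birth control (one of which must include a condom as a barrier method of contraception"), beginning at screening and "continuing throughout the course of treatment and for at least three months after ESK981 is discontinued". The section says that the effect in pregnancy is not known, and gives as its reason that "ESK981 can cause fetal harm when administered to a pregnant woman based on its mechanism of action".

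Neither section refers to the other. The nearest general provision is section 3.1.2, which asks a participant to "Be willing and able to adhere to the prohibitions and restrictions specified in this protocol"; it does not mention contraception or any period.

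**The concern.** An eligibility criterion is where a site confirms that a participant accepts a precaution. Here it confirms less than the safety section of the same protocol advises. A man willing to use one non-barrier method and to stop 30 days after his last dose passes 3.1.9, yet falls short of section 7.5 on the number of methods, the condom, the start and the duration. An investigator counselling him could give either instruction and point to the protocol for it.

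What is at stake is the protection of partners and of a possible pregnancy, not the efficacy result. Section 7.5 treats a partner's pregnancy as an event to be reported to the sponsor as an SAE within 24 hours, so the protocol itself regards the risk as worth guarding against.

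**Working it through.** No statistical figure is involved. The check sets the two provisions side by side and sizes the differences.

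| Element | Section 3.1.9 | Section 7.5 |
|---|---|---|
| Status | Inclusion criterion, met at registration | Advice to men receiving ESK981 |
| Methods | One, chosen by the investigator's judgement | Two |
| Condom | Not named | Must be included |
| Start | Treatment period | Screening |
| Minimum after last dose | 30 days | Three months |

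**Gap after the last dose.** Three calendar months are 89 to 92 days. 89 − 30 = 59 and 92 − 30 = 62, so the gap is 59 to 62 days.

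**Difference at the start.** The Study Calendar (Appendix C) puts screening at Day -28 to Day -1, so section 7.5 can begin up to 28 days earlier. No ESK981 is given in that time, so this difference adds no drug exposure.

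**Pharmacokinetic context.** Section 1.1 states: "Clinical testing demonstrated linear dose-related oral exposure in humans with 8-15 h half-life". Thirty days are 30 × 24 = 720 hours.

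- At 15 h: 720 / 15 = 48 half-lives.
- At 8 h: 720 / 8 = 90 half-lives.
- At 20.6 h, the longest individual value shown in Table 2: 720 / 20.6 = about 35 half-lives.

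These figures suggest that a case for 30 days could be made. The protocol does not make it, and it gives no reason for three months either.

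**Is there a later safeguard?** The Study Calendar lists no contraception check at any visit. The end-of-treatment visit falls 30 days after the last dose, which is when the 3.1.9 minimum expires. Follow-up every three months after that (section 4.2) collects survival status and subsequent anti-cancer therapy. Section 7.5 asks the participant to report a partner's pregnancy, but no scheduled contact prompts him to do so in the two months at issue. In the reviewed text, registration is therefore the only scheduled check.

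**The case against.** The strongest reply is that the two provisions do not conflict. Both periods are minimums; 3.1.9 sets a floor for entry and section 7.5 adds fuller advice for treated men. Anyone who follows section 7.5 also meets the period in 3.1.9, so a site can apply both without a rule of precedence. Changing 3.1.9 would alter only what a man declares at entry, since neither section provides for checking use after the last dose. An investigator could also decide that only the section 7.5 approach counts as effective. Sections 3.1.2 and 3.1.10, and the risk counselling required by section 3, give further routes by which the advice could reach participants, as does the consent form, which was not available for review.

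The risk itself also looks low. Each participant "must have a castrate serum testosterone level" and metastatic disease, and the half-life is short. The statement on fetal harm concerns a drug given to a pregnant woman, whereas only men are enrolled. Neither period is justified, so it can be argued that the documents do not establish which should give way.

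Much of this stands: there is no strict contradiction, the number affected is probably small, and harm in the extra two months is not shown. It does not remove the mismatch. None of the general provisions names contraception or a period, and a reader given a specific criterion in 3.1.9 will apply that one. Leaving the method to the investigator's judgement does not change the 30-day minimum.

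**Conclusion.** The concern holds. The contraception standard checked at registration is weaker than the one the protocol advises: one method against two, no condom named against one required, and a post-treatment minimum shorter by 59 to 62 days. No text reconciles the two.

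Practical impact is low. The documents give no count of men affected, no data on exposure through a male partner, and no reason for either period. The conclusion therefore rests on the wording alone and assumes no proven exposure in the extra two months. The removed consent pages may carry the fuller instruction; that could not be checked, and it would not change what 3.1.9 asks for. The primary endpoint, sample size and analyses are unaffected. The point should be corrected because it concerns an operative eligibility rule and costs little to put right.

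**What to change.** Amend 3.1.9 to the section 7.5 standard: willingness to use two acceptable methods, one of them a condom, from screening, throughout treatment, and for at least three months after the last dose of ESK981. This is the more cautious choice while no reason for 30 days is on record.

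If the sponsor considers 30 days sufficient, it should document the reason, drawing on the pharmacokinetics and any reproductive-toxicity information it holds, and amend the period in section 7.5 to match.

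In either case, check that the consent form states the same methods and period. The cost is a protocol wording amendment, plus a consent revision if that wording differs. No visit, sample size or analysis changes.

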3.2 Exclusion Criteria

- 3.2.1 Current systemic therapy (other than a GnRH agonist/antagonist) for CRPC including:
 - a. CYP-17 inhibitors (e.g. ketoconazole, abiraterone)
 - b. Antiandrogens (e.g. bicalutamide, nilutamide)
 - c. Second generation antiandrogens (e.g. enzalutamide, ARN-509, Galetterone)
 - d. Immunotherapy (e.g. sipuleucel-T, ipilimumab)
 - e. Chemotherapy (e.g. docetaxel, cabazitaxel)
- 3.2.2 Prior chemotherapy (e.g. docetaxel, cabazitaxel) for CRPC. Prior docetaxel administered in the castrate-sensitive space is allowed.
- 3.2.3 Prior radiopharmaceutical therapy (e.g. radium-223, strontium-89, samarium-153, etc.) within the past year.
- 3.2.4 Have any condition that, in the opinion of the investigator, would compromise the well-being of the subject or the study or prevent the subject from meeting or performing study requirements.
- 3.2.5 The patient has any of the following hematologic values:
 - absolute neutrophil count (ANC) less than 1500/mm³
 - platelet count less than 100000/mm³
 - hemoglobin less than 9 g/dL.
- 3.2.6 The patient has any of the following hepatic function values:
 - bilirubin greater than 1.5 times the upper limit of normal (ULN)
 - alanine aminotransferase (ALT) greater than 2.0 times the ULN in the absence of known hepatic metastases
 - aspartate aminotransferase (AST) greater than 2.0 times the ULN in the absence of known hepatic metastases,
 - ALT or AST greater than 3.0 times the ULN in the presence of known hepatic metastases.
- 3.2.7 The patient has a serum creatinine value greater than 1.5 mg/dL.
- 3.2.8 The patient has active brain metastases.

- 3.2.9 The patient is currently on warfarin or heparin therapy.
- 3.2.10 The patient has any pre-existing coagulopathy, recent hemoptysis, gross hematuria or gastrointestinal bleeding.
- 3.2.11 The patient has a history of a clinically significant cardiovascular or cerebrovascular event within 6 months prior to study entry.
- 3.2.12 The patient has uncontrolled hypertension defined as a blood pressure measurement greater than 150 mm Hg systolic or 90 mm Hg diastolic with medication.
- 3.2.13 The patient has received any investigational drug within the past 4 weeks.
- 3.2.14 The patient has previously been enrolled in the study or received ESK981.
- 3.2.15 The patient has known hypersensitivity to gelatin or lactose monohydrate.
- 3.2.16 The patient has taken a medication known to be a potent inducer of CYP1A2, CYP2C8, or CYP3A4 within 4 weeks prior to the first dose of study drug.
- 3.2.17 The patient has taken a medication known to be a potent inhibitor of CYP1A2, CYP2C8, or CYP3A4 within 2 weeks prior to the first dose of study drug.

